4.9 Efficacy Variables

4.9.1 TETRAS

The TETRAS is a scale used to quantify essential tremor severity and its impact on activities of daily living (ADLs). The full scale consists of 2 components, the Performance and ADL subscales which are highly correlated. Upper extremity action tremor is the main focus of both parts of this scale since it is the main source of disability. However, action tremor is also assessed in the head, face, voice, and lower limbs.

4.9.1.1 Performance subscale

The performance subscale consists of 9 items covering different body regions. Each item is rated on a scale of 0 to 4, including 0.5 increments if a rating cannot be reconciled between two whole numbers, with higher scores indicating higher tremor amplitude. Item 4 of the performance subscale is the upper limb item. It is comprised of 6 sub-items (4a, 4b, and 4c assessed for both the right and left upper limbs). The upper limb total score is the sum of these 6 items and ranges from 0 to 24. The timepoint, blinded TETRAS code, date and time of assessment, rater ID, an indicator of whether the assessment was performed (Yes/No), and the individual item scores will be recorded in the eCRF.

The full performance subscale score is calculated as the sum of item 1 (head), item 2 (face), item 3 (voice), each of the 6 sub-items for item 4 (upper limb), the maximum of the 4 sub-items for item 5 (lower limb), 2 sub-items (right and left side) for item 6 (Archimedes spirals), item 7 (handwriting), 2

sub-items (right and left side) for item 8 (dot approximation), and item 9 (standing) for a total score ranging from 0 to 64 from 16 sub-items.

The TETRAS performance subscale will be collected at the following timepoints:

Part A:

- Screening, Day 0 and Day 21: completed anytime
- Day 1: pre-dose and 6 (± 2) hours post-dose
- Day 7 and Day 14: 6 (± 2) hours post-dose

Part B:

- Screening and Day 70: completed anytime
- Day 1: pre-dose and 6 (± 2) hours after a 20 mg qAM dose
- Day 7: 6 (± 2) hours after a 40 mg qAM dose
- Day 21: 6 (± 2) hours after an 80 mg (or highest tolerated dose) qAM dose
- Day 42: pre-dose and 6 (± 2) hours after a 120 mg (or highest tolerated dose) qAM dose

4.9.1.2 Upper limb item

The upper limb item will be assessed via clinician (ie, site rater), Kinesia ONE (accelerometer), and video rating by an independent rater. In Item 4 of the performance subscale, the clinician will assess 3 tasks performed on each side of the body: 4a) postural tremor with upper limbs held forward and horizontally (“outstretched” position), 4b) postural tremor with upper limbs extended laterally and horizontally, with the elbows flexed and hands positioned close to each other near the chin (“wing beating position”), and 4c) kinetic tremor during finger-nose (or chin)-finger movements. As each of the upper limb items is rated independently for the right and left side of the body, the upper limb item is comprised of 6 sub-items. Each sub-item is rated on a scale from 0 to 4 including 0.5 increments, with higher scores indicating higher tremor amplitude of the upper limb. The upper limb total score is the sum of these 6 sub-item scores and ranges from 0 to 24. The baseline TETRAS upper limb score will be categorized as <10 or ≥ 10 .

4.9.1.3 Combined upper limb

The combined upper limb score is the sum of the 6 sub-item scores of the upper limb item and the handwriting and spirals scores. The combined upper limb score ranges from 0 to 32.

4.9.1.4 Accelerometer

After the TETRAS Performance Subscale is performed by the clinician, the participant will then perform the TETRAS upper limb tasks while wearing a Kinesia ONE accelerometer. The accelerometer will record coordinates and accelerations in the 3D space over time. All 3 maneuvers in the upper limb assessments will be completed for both arms, first for the right arm and then for the left. Kinesia ONE assessments should be completed twice at each timepoint with the 2 assessments separated by at least 30

minutes. The timepoint, date and time of both assessments, and an indicator of whether the accelerometer assessment was performed (Yes/No) will be recorded in the eCRF.

Each upper limb sub-item is scored on a scale from 0 to 4 including to 0.1 increments and will be provided by the Kinesia ONE accelerometer vendor. The accelerometer upper limb total score, ranging from 0 to 24, is the sum of these 6 sub-items and ranges from 0 to 24. For each timepoint, the average score of the two Kinesia ONE assessments will be calculated to be used for analysis. If only one assessment is performed, the single score will be used for analysis.

4.9.1.6 Telehealth Assessment

The TETRAS Performance Subscale upper limb item (item #4) will be conducted by the site rater using televideo technology while the participant is at home. The date and time of telehealth assessment, rater ID, an indicator of whether the assessment was performed (Yes/No), and the individual item scores will be recorded in the eCRF. The upper limb score will be calculated as the sum of all 6 sub-items.

4.9.1.7 Activities of Daily Living (ADL)

The TETRAS ADL subscale is a 12-item assessment of typical daily activities that are impacted by tremor that will be collected for Part B only. Activities are assessed in the following functional domains: speaking, feeding, drinking, personal hygiene, dressing, writing, and social activity. The impact to each function is rated on a 5-point Likert scale from 0 to 4. The ADL subscale score is calculated as the sum of all 12 items and ranges from 0 to 48 with higher scores reflecting higher impact. The date and time of the ADL subscale, rater ID, an indicator of whether the assessment was performed (Yes/No), and the individual item scores will be recorded in the eCRF. The subscale score will be derived directly in the eCRF.

4.9.4 Quality of Life in Essential Tremor Questionnaire (QUEST)

The QUEST is a patient-reported ET-specific quality of life scale that will be collected for Part B only. The scale contains 5 subscales that cover physical, psychosocial, communication, hobbies/leisure, and work/finance dimensions. The individual items are rated either on a 5-level Likert scale from 0 to 4 (Never, Rarely, Sometimes, Frequently, Always) or a 2-level scale from 0 (No) to 4 (Yes) relative to the respondent's current situation. Five items could also be rated as not applicable. The QUEST total and subscale scores are calculated as the sum of all applicable items divided by the number of applicable items times 100. The subscale scores will be derived directly in the eCRF.

Participants are also asked to rate their overall health status and quality of life on scale from 0 to 100 by 5 point increments, if tremor has interfered with their sexual satisfaction (Yes/No), if they have had side effects from tremor medication (Yes/No), if they are satisfied by tremor control achieved by tremor medication (Yes/No), and to describe their work status (Never Worked, Not working, retired because of tremor, Not working, retired NOT due to tremor, Working full time, Working part time). Additionally, the participant is asked to report how many hours in a typical day they experience tremor in any body part (0 to 24) and the severity of tremor in the head, voice, right arm/hand, left arm/hand, right leg/foot, and left leg/foot on a scale from 0 to 4 (None, Mild, Moderate, Marked, Severe).

An indicator of whether the QUEST was performed (Yes/No), the date and time of assessment, rater ID, and individual item scores will be recorded on the eCRF.

- IF the action taken with study drug is “Study drug withdrawn”, THEN set the AE leading to study drug withdrawal flag equal to “Y”.
- OTHERWISE, set the AE leading to study drug withdrawal flag equal to “N”.

Treatment emergent AEs (TEAEs) are defined as those AEs occurring or worsening after the first dose of study drug. If an AE start date is completely missing (ie, in which the day, month, and year are all unknown), then the AE start date will be set to the date of first dose of study drug. For a partial AE start date, the following conventions will be used for imputing the AE start date:

- When the year is present and the month and day are missing:
 - If the year of AE start = the year of first dose of study drug, then the month and day will be set to the month and day of first dose of study drug.
 - If the year of AE start < the year of first dose of study drug, then the month and day will be set to December 31st.
 - If the year of AE start > the year of first dose of study drug, then month and day will be set to January 1st.
- When the year and day are present and the month is missing:
 - If the year of AE start = the year of first dose of study drug, then the month will be set to the month of first dose of study drug.
 - If the year of AE start < the year of first dose of study drug, then the month will be set to December.
 - If the year of AE start > the year of first dose of study drug, then the month will be set to January.
- When the month and year are present and the day is missing:
 - If the year of AE start = the year of first dose of study drug and

- the month of AE start = the month of first dose of study drug, then the day will be set to the day of first dose of study drug.
- the month of AE start < the month of first dose of study drug, then the day will be set to the last day of the month.
- the month of AE start > the month of first dose of study drug, then the day will be set to the 1st day of the month.
- If the year of AE start < the year of first dose of study drug, then the day will be set to the last day of the month.
- If the year of AE start > the year of first dose of study drug, then the day will be set to the 1st day of the month.
- If the imputed AE start date is after the AE stop date, then the AE start date will be set to the AE stop date.

For Part B, AEs will be identified as TEAEs for the double-blind randomized withdrawal phase based on the first dose of randomized study drug. AEs reported during the open-label titration period will not include events occurring within the randomized withdrawal phase. Events occurring within the safety follow-up period for a participant will be classified as occurring during his/her last phase of participation (ie, if a participant does not enter the double-blind randomized withdrawal phase any post-treatment AEs will be reported as part of the open-label titration).

If an AE is imputed for Part B and is attributed to the open-label titration or double-blind randomized withdrawal phase, it should be checked for plausibility. If an imputed AE onset date could potentially have started during a subsequent phase (eg, if the onset date had been imputed as the 1st of a particular month falling into the open-label titration phase, but it plausibly could have started later in the month during the double-blind randomized withdrawal phase), the AE should be identified as TEAE for any plausible phases.

For each AE, a treatment emergent flag will be calculated using the recorded AE start date (or imputed start date, where applicable). Additional treatment emergent flags will be created for each dose level.

Adverse events occurring during PRAX-944 titration will be assigned to a dose level based on the onset date/time of the adverse event relative to the first dose date/time of study drug administration at each dose level. Specifically, if an AE occurs after the first dose of study drug at a participant's actual dose level and prior to the first dose at the next dose level, the AE will be assigned within a participant's actual dose level in the adverse event summary. If the date was imputed and could plausibly occurred during a subsequent dose level, the AE should be identified as TEAE for subsequent and plausible dose levels.

If the time is missing (either for the adverse event or study drug administration), then the AE date (and relative study day) will be used to determine in which dose level the AE should be assigned, assuming that the AE occurred after the dose taken on the specified day. An adverse event will only be reported within the dose level in which the AE started (eg, an adverse event that starts within the 40 mg dose level and continues into the 80 mg dose level will only be reported in the 40 mg dose level).

[figure not shown]
In addition, each AE will also be categorized into the study period in which it started: prior to first dose (ie, Screening/Baseline period), during the Intervention period (Part A), open-label titration phase (Part

B), double-blind randomized withdrawal phase (Part B), or during the Safety Follow-up period. AEs categorized under multiple study periods will be identified as needed. AEs starting during the Safety Follow-up period will be defined as any event with a start date occurring after the last date in the Intervention Period, according to the SoAs for each respective study part. AEs with an onset after Day 56 will be reported based on the last dose level received during the study and last phase of participation (open-label titration or double-blind randomized withdrawal phase).

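### When only the month of an AE start date is missing, the SAP's imputation rule can date a possible on-study onset before first dose and drop it from the TEAE summaries

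*SAP*

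**What the plan says.** All the rules at issue are in SAP 4.10.1 (Adverse Events).

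- Definition: "Treatment emergent AEs (TEAEs) are defined as those AEs occurring or worsening after the first dose of study drug".
- Flag: for each AE "a treatment emergent flag will be calculated using the recorded AE start date (or imputed start date, where applicable"), so the imputed date decides the classification.
- Branch at issue: "When the year and day are present and the month is missing" and the AE year equals the first-dose year, "then the month will be set to the month of first dose of study drug". The recorded day is kept. No condition compares the result with the first-dose date.
- Completely missing date: "then the AE start date will be set to the date of first dose of study drug".
- Year only, same year: "then the month and day will be set to the month and day of first dose of study drug".
- Month and year known, both equal to those of first dose: "then the day will be set to the day of first dose of study drug".
- Closing adjustment: "If the imputed AE start date is after the AE stop date, then the AE start date will be set to the AE stop date".

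The same section later asks for a plausibility check on imputed dates. The phase version is limited to Part B AEs already attributed to the open-label titration or the double-blind withdrawal phase. The dose-level version sits in a paragraph about AEs occurring during titration.

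**The concern.** Where the recorded fragments leave onset on the first-dose date possible, the other branches place the AE on that date, so doubt counts towards treatment emergence. The missing-month branch does not do this. It can produce a pre-dose date when a later month of the same year fits the record equally well.

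The closing stop-date adjustment only moves a start date earlier, so it cannot bring such an AE back. An AE dated into Screening/Baseline also fails the opening condition of the Part B phase check, and Part A has no phase check.

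At stake are the summaries restricted to TEAEs in SAP 5.8.1 and its subsections: incidence, drug-related events, events leading to study drug withdrawal, and maximum severity. Part B's primary objective is safety and tolerability, with approximately 12 and at most 24 participants. One participant is therefore 1/24 = 4.2 to 1/12 = 8.3 percentage points of an incidence.

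**Working it through.** The plan gives no figure for this point, so there is none to reproduce. The check applies the rule literally.

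**Inputs.** Study day follows SAP section 4: date minus first-dose date, plus 1 if on or after first dose, with no Day 0. Part A dosing is Days 1–14 with follow-up to Day 21. Part B dosing is Days 1–56 with follow-up to Day 70. AEs are collected from consent (SAP 4.10.1). First-dose dates are assumed uniform over one calendar year (2021 used).

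**Single case.** First dose 20 September; AE recorded as day 05, month unknown, same year.
- The rule gives 5 September: 5 − 20 = Day −15, not a TEAE.
- 5 October: 15 + 1 = Day 16. In Part B this is a dosing day. In Part A it falls in follow-up, which is still after first dose and so treatment-emergent.
- 5 November: 46 + 1 = Day 47, also a Part B dosing day.
- If consent was on 10 September, the imputed date even precedes AE collection. The only in-study candidates in Part B are then Days 16 and 47, both after first dose.

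**How often a true on-treatment onset is dated pre-dose.** Take every first-dose date in the year and every dosing day in the same year, delete the month, and apply the rule.
- Part B: 365 × 56 − (56 × 55)/2 = 20,440 − 1,540 = 18,900 onsets. Dated pre-dose: 8,083, and 8,083/18,900 = 43%.
- Part A: 365 × 14 − (14 × 13)/2 = 5,110 − 91 = 5,019 onsets. Dated pre-dose: 1,001, and 1,001/5,019 = 20%.
- With follow-up included, the shares are 9,713/23,135 = 42% (Part B, to Day 70) and 2,310/7,455 = 31% (Part A, to Day 21).

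**How often a later date is possible at all.** The rule gives a pre-dose date whenever the AE day is smaller than the first-dose day. The number of such combinations in the year is 7 × 465 + 4 × 435 + 378 = 5,373.
- Part B: 4,905 of 5,373 (91%) have another same-year month that falls on a dosing day. For first doses in January to November it is 4,905 of 4,908. The remaining 465 combinations are December first doses, which have no later month in the same year.
- Part A: 1,001 of 5,373 (19%) have a same-year date on Days 1–14, and 2,310 of 5,373 (43%) have one by Day 21. In the other 57% no date from first dose to Day 21 fits, so the pre-dose date is the reasonable one.

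**The case against.** **The plan has plausibility checks.** SAP 4.10.1 asks for an imputed Part B AE to be counted in any later phase in which it could have started, and for AEs falling in several study periods to be identified as needed. This shows the intent. But the phase check opens with AEs already attributed to a Part B treatment phase, the dose-level check concerns AEs during titration, and the last sentence gives no rule. Coverage of a pre-dose imputation is arguable at best in Part B, and Part A has no phase check.

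**Genuine pre-dose AEs exist.** AEs are collected from consent, and Screening can last 28 days, or 42 with primidone withdrawal. This stands, and it rules out a tempting figure. With AE day and dosing day independent and uniform on 1–30, the AE day is the smaller in 435/900 = 48% of cases. A reader might take that as a misclassification rate. It is not, because it includes AEs that truly began before dosing and it does not separate the two parts.

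**Moving every such AE to the first-dose date would overcorrect.** This also stands. With first dose on 20 September in Part A and AE day 15, the next candidate, 15 October, is Day 26. That is after the study ends at Day 21 (±1), so the onset was before dosing. A blanket move would create a false TEAE. It would also discard the known day and assign the AE to the 20 mg level; in the Part B single case the first compatible date, Day 16, falls at 80 mg on the planned schedule.

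**The consequence is limited.** The Part B endpoint is worded as incidence and severity of AEs. The overview rows in SAP 5.8.1 for SAEs, AEs leading to death and AESIs are not labelled as TEAE-only. All AEs are listed, no safety hypothesis is tested, and an AE that worsens after first dose remains a TEAE by definition. All of this stands.

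**Conclusion.** The gap is real on the literal text, and small. It needs four things together: day and year known, month missing, AE year equal to first-dose year, and AE day earlier than first-dose day. Within the missing-month pattern, about 43% of true same-year on-treatment onsets in Part B and 20% in Part A would be dated pre-dose. These shares rest on onset uniform over dosing days and first doses uniform over one assumed calendar year. They are conditional on the pattern, for which the documents give no frequency; it is probably rare in a study this short with frequent contacts.

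A reader might infer that the rule materially undercounts the Part B primary endpoint or hides AEs from the report. The documents do not support that. The loss is confined to the TEAE summaries, the AE remains in the listings, and for many Part A date combinations the pre-dose date is correct. It is a minor point, worth settling because it is cheap and because one event is visible in a sample of 12 to 24.

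**What to change.** Add to the missing-month, same-year branch of SAP 4.10.1: if the imputed start date is before first dose, and a later month compatible with the recorded day, the year and any stop date falls within the participant's AE collection period, set the start date to the first such date on or after first dose and flag the AE as treatment-emergent; otherwise keep the pre-dose date.

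Extend the plausibility check on imputed dates in the same section to Part A and to AEs imputed into Screening/Baseline.

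The cost is a few lines of SAP text and a matching programming condition, to be settled before database lock. No data collection changes. The downside is that a few AEs that truly began before dosing may be counted as TEAEs, which is the direction the other branches already take.

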The Safety Follow-up period will take place from Day 57 to Day 70. At the end of the Safety Follow-up period, participants will return to the clinic on Day 70 for the final clinical trial assessments (Table 3).

Safety Monitoring

The Sponsor will review ongoing safety data. The clinical trial may be stopped, or clinical trial enrollment suspended if:

- The Sponsor, in consultation with the Principal Investigators, consider that the number and/or severity of AEs justify discontinuation of the clinical trial
- The Sponsor makes a decision to do so

Critical safety endpoints are listed in [Section 8.2](#). AEs and concomitant medication and procedures use will be monitored from the time of informed consent to Day 21 (± 1 day) in Part A and to Day 70 in Part B. At that time, participants will have completed the clinical trial.

Renal function monitoring will be based on the KDIGO criteria for acute kidney injury (AKI) as outlined in [Section 8.2.4.1](#). If a participant's laboratory values exceed these thresholds, dosing of that participant will be stopped, and the laboratory tests repeated.

NUMBER OF PARTICIPANTS**Part A**

Up to 12 participants are planned to be administered PRAX-944.

Part B

Approximately 12 participants are planned to be administered PRAX-944 for the first 42 days followed by randomization (1:1) to 2 additional weeks on the highest tolerated dose of PRAX-944 or placebo. Up to 12 additional participants may be enrolled at the discretion of the Sponsor to ensure inclusion of a broad range of tremor severity.

Participant Replacement

Participants who withdraw from either Part A or Part B prior to completion of the clinical trial may be replaced at the discretion of the Sponsor. No more than 6 participants in either part of the study will be replaced.

DURATION OF CLINICAL TRIAL

Participants will be part of the clinical trial for the following time intervals:

Part A

Screening/Baseline Period	Up to 28 days (+14 days if on primidone)
Intervention Period	14 days
Safety Follow-up Period	7 days

Total Participation	Up to 49 days (63 days if on primidone)
---------------------	---

Part B

Screening/Baseline Period	Up to 28 days (+14 days if on primidone)
Safety Follow-up Period	14 days
Total Participation	Up to 98 days (112 days if on primidone)

INCLUSION/EXCLUSION CRITERIA**Inclusion Criteria**

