Visit Days (Visit Window)	Day -28 to Day -1		Day 1 (Baseline)	Day 3	Day 7	Day 14	Day 21	Day 28	Day 35	Day 41	Day 42	Day 56	Day 70/ET (End of Clinical Trial)
		Day -2 (-2)											

Performance timepoints or accelerometer-based assessment timepoints, the PK sample is to be obtained last. On Days 7, 21, and 56; samples should be collected 2 hours post-dose. Blood collection can be completed anytime on Day 70.

^j Participants will be randomized (1:1) to receive either placebo or PRAX-944 from Day 43 to Day 56. Randomization can occur on Day 37 through Day 42.

^k On Day 1 and 42, study drug must be administered in the clinic on an empty stomach (at least 1 hour before breakfast, which will be provided at the site) and the participant should be observed in the clinic for approximately 6 hours before discharge. On all other days, participants should be instructed to take study drug at least 1 hour before breakfast in the morning at home. The escalation schedule is as follows: 20 mg, Day 1 through Day 3; 40 mg, Day 4 through Day 7; 60 mg, Day 8 through Day 14; 80 mg, Day 15 through Day 21; 100 mg, Day 22 through Day 28; and 120 mg, Day 29 through Day 42. Participants will receive blinded study drug on Days 43 to 56. During blinded treatment period, participants should take the same number of tablets per day as taken during Days 36 to 42.

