- c. Placement of an intrauterine device or intrauterine system.

Note:

- A participant can agree to using 2 methods, 1 of which is primarily dependent on their partner. For example, a male participant can agree to a barrier with spermicide and for his female partner to use oral hormonal contraception. Similarly, a female participant can agree to using oral hormonal contraception and for her male partner to use a barrier with spermicide.
- Male participants must use 2 highly effective methods from Day -1 through 90 days + 5 half-lives (3 days) after the last dose of study drug (ie, 93 days).
- Female participants must use 2 highly effective methods from Day -1 through 30 days + 5 half-lives (3 days) after the last dose of study drug (ie, 33 days).

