5 ANALYSIS METHODS

Analysis will be carried out using SAS® (version 9.4 or newer, SAS Institute Inc, Cary, NC). Templates for the summary tables, figures, and participant data listings will be available separately. Data listings will include all data recorded for all enrolled participants; where captured, data entered for screen failure participants will be flagged in the listings.

For all data displays, separate summaries will be generated for each part and phase (open-label titration and double-blind randomized withdrawal) of the clinical trial.

- Part A: All summaries except those for adverse events will use a single "PRAX-944 Overall" column. Summaries of adverse events will use the following columns: "PRAX-944 20 mg qAM", "PRAX-944 40 mg qAM ", and "PRAX-944 Overall".
- Part B: Summaries of disposition and PK will be presented for all of Part B (i.e., not by phase) and will use a single "PRAX-944" column.
- Part B Open-label Titration: Summaries of demographics, baseline characteristics, medical history, prior and concomitant medications, study drug exposure, efficacy, and all safety except adverse events will include a "PRAX-944 Overall" column. Summaries of adverse events will include columns for "PRAX-944 20 mg qAM", "PRAX-944 40 mg qAM ", "PRAX-944 60 mg qAM ", "PRAX-944 80 mg qAM ", "PRAX-944 100 mg qAM ", "PRAX-944 120 mg qAM ", and "PRAX-944 Overall".
- Part B Randomized Withdrawal: Summaries of demographics, baseline characteristics, medical history, prior and concomitant medications, study drug exposure, efficacy, and all safety except adverse events will include the columns "Placebo" and "PRAX-944" for the randomized withdrawal phase. Summaries of adverse events will include columns for "Placebo" and "PRAX-944".

Descriptive statistics for continuous data will include number of participants (n), mean, standard deviation (SD), median, minimum, and maximum. Summaries of change from baseline variables will include only participants who have both a baseline value and corresponding value at the timepoint of interest. Descriptive statistics for categorical data will include frequency and percentage. Where appropriate, descriptive statistics may be presented with 95% confidence intervals (CIs).

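### Part B adverse events starting after dosing ends (Days 57-70) are counted inside the Placebo and PRAX-944 columns, which dilutes the trial's only placebo-controlled AE comparison

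*SAP*

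**What the plan says.** The footnotes to the Part B schedule (Protocol 1.3) give the blinded dosing window: "Participants will be randomized (1:1) to receive either placebo or PRAX-944 from Day 43 to Day 56". The Protocol synopsis gives the next period: "The Safety Follow-up period will take place from Day 57 to Day 70". No study drug is given in that second period.

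SAP 4.10.1 opens the treatment-emergent window at the start of blinded dosing: "AEs will be identified as TEAEs for the double-blind randomized withdrawal phase based on the first dose of randomized study drug". It then states the follow-up rule twice, once by period ("Events occurring within the safety follow-up period for a participant will be classified as occurring during his/her last phase of participation") and once by day ("AEs with an onset after Day 56 will be reported based on the last dose level received during the study and last phase of participation").

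SAP section 5 plans separate Part B AE summaries for the titration and withdrawal phases only. The withdrawal summaries have one Placebo column and one PRAX-944 column. SAP 4.10.1 also derives, for each AE, the study period in which it started, and Safety Follow-up is one of the categories. None of the AE summaries described in SAP 5.8.1 uses that variable.

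**The concern.** In many parallel-group trials it does little harm to count follow-up events under the last treatment. Here, stopping PRAX-944 is the randomized manipulation. The placebo arm takes its last active dose on Day 42 and the PRAX-944 arm on Day 56. The planned table runs to Day 70 for both, so each arm's column contains the two weeks after that arm stopped the drug.

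Two things follow. An excess of AEs on continued drug is diluted, because half of the PRAX-944 column's calendar window lies after dosing. An excess of AEs caused by stopping is hidden to some degree, because it can appear in both columns. Worsening tremor is a concrete possibility. Tremor is among the preferred terms for AEs of special interest (SAP Appendix 2), and exacerbation of a pre-existing condition can qualify as an AE (Protocol Appendix 2, subject to its exclusion of expected disease symptoms).

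Safety is the primary objective of Part B, and Part A and the Part B titration are open-label. This is the only AE table with a concurrent placebo arm, and its columns do not correspond to a single exposure state.

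**Working it through.** **Windows.** Blinded dosing is 56 − 43 + 1 = 14 days. Follow-up is 70 − 57 + 1 = 14 days. These reproduce the protocol's stated Part B participation: screening 28 + titration (3 + 4 + 7 + 7 + 7 + 14 = 42) + 14 + 14 = 98 days, or 112 with the 14 extra screening days for primidone.

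**What each column covers (Days 43-70, 28 days).** Protocol 5.4.3 equates 5 half-lives with 3 days: "Female participants must use 2 highly effective methods from Day -1 through 30 days + 5 half-lives (3 days) after the last dose".

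| Column | Dosing with PRAX-944 | After last PRAX-944 dose | Drug-free after 3-day washout |
|---|---|---|---|
| PRAX-944 | 14 | 14 (50%) | 14 − 3 = 11 (11/28 = 39%) |
| Placebo | 0 | 28 (100%) | 28 − 3 = 25 (25/28 = 89%) |

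**Dilution of an on-drug effect.** Assumption (the documents give no rates): hazard 0.05 per day while exposed and 0.02 per day otherwise, with the 3 washout days counted as exposed. Incidence = 1 − exp(−cumulative hazard).

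| Window | PRAX-944 | Placebo | Ratio |
|---|---|---|---|
| Days 43-56 | 14 × 0.05 = 0.70, giving 50% | 3 × 0.05 + 11 × 0.02 = 0.37, giving 31% | about 1.6 |
| Days 43-70 (planned) | 17 × 0.05 + 11 × 0.02 = 1.07, giving 66% | 3 × 0.05 + 25 × 0.02 = 0.65, giving 48% | about 1.4 |

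The absolute difference hardly moves: 50 − 31 = 19 points against 66 − 48 = 18 points.

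**Offset of an AE caused by stopping.** Let w be the assumed probability of such an AE, b the background probability per 14 days, and suppose every such AE starts within 14 days of stopping, with no additional on-drug AEs.

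- Days 43-56: Placebo 1 − (1 − w)(1 − b); PRAX-944 b.
- Days 43-70: both columns 1 − (1 − w)(1 − b)².

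| w | Difference, Days 43-56, b = 0 | Difference, Days 43-56, b = 10% | Planned difference, either b |
|---|---|---|---|
| 15% | 15 points | 13.5 points | 0 |
| 30% | 30 points | 27 points | 0 |
| 50% | 50 points | 45 points | 0 |

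If only half of these AEs start within 14 days and the rest in Days 15-28 after stopping, the offset is partial. For w = 30% and b = 0, the Placebo column shows 30% and the PRAX-944 column 15%, so the planned difference is 15 points and the other 15 are offset.

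**The case against.** The rule is a declared convention with a purpose: no post-dose event drops out of the tables. The C-SSRS summary in SAP 5.8.5 likewise counts from dosing through follow-up. Nothing is lost. All AEs are listed by participant, the onset period is derived, and with about 12 participants (at most 24) a reader could sort events around Day 56 by hand. The table templates are held separately, so a split shell cannot be ruled out. SAP 5.8 excludes formal testing of safety variables. With about 6 to 12 per arm, one participant moves incidence by 1/6 = 17 points or 1/12 = 8 points, so neither window supports a firm contrast. Laboratory, vital-sign and ECG results are summarized by visit and are not affected.

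All of that stands, and it limits how much the point matters. It does not alter what the SAP text specifies, which is a pooled table with no follow-up display.

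A reader might go further and infer that discontinuation AEs will occur and cancel between arms. The documents do not support that. The risks described in Protocol 2.4 (partly redacted) include no withdrawal or rebound event, and full offset requires every such event to start within 14 days of stopping. A reader might also take half of the PRAX-944 window as drug-free. That counts dosing days only and overlooks the protocol's own washout figure. Ignoring washout likewise exaggerates the hazard illustration: 50% against 24% for Days 43-56 and 62% against 43% for Days 43-70, a fall in ratio from 2.1 to 1.5.

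**Conclusion.** The point holds as a reporting defect. The SAP's rule puts AEs from 14 post-dosing days into the PRAX-944 column, 11 of the 28 days (39%) being drug-free after washout, beside a Placebo column made up wholly of days after stopping PRAX-944. That dilutes the only placebo-controlled AE comparison, and it allows an AE caused by stopping to be counted in both arms.

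The pooling rule and the day counts come directly from the documents. The size of the effect does not: the fall in ratio from about 1.6 to 1.4, and the offset of anything from part to all of a discontinuation effect, rest on assumed rates and onset times. No test, power figure or decision rule changes, and the events can still be separated from the listings. The case for changing the plan is that the table would otherwise be hard to interpret, and that the correction is cheap.

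**What to change.** In SAP 4.10.1 and 5.8.1:

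- Tabulate randomized-withdrawal AEs by arm with onset from the first through the last blinded dose (Day 56 for completers), optionally extended by the 3-day washout. State the chosen cut-off.
- Show AEs with follow-up onset by arm in a separate block, using the study-period variable already derived. Label the PRAX-944 follow-up block as after stopping, so that it can be read beside the placebo arm's Days 43-56.
- Keep the combined Day 43-70 total as an additional row, so that no event leaves the tables.
- The derived period variable is cut at the scheduled end of the Intervention Period. State whether that date or the actual last blinded dose governs for a participant who stops early.

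The cost is SAP wording and one extra table block, with no new data. The downside is that a drug effect with onset shortly after the last dose may fall in the follow-up block, where it is still shown by arm; the washout extension reduces this.
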